1 PROTOCOL SUMMARY

1.1 SYNOPSIS

Title:	Rapid Acceleration for Diagnostics in Underserved Populations: Home Testing (RADx-UP HoT)
Study Description:	This observational, cohort sub-study is embedded within a larger public health intervention that distributes at-home, self-administered, SARS-CoV-2 antigen testing kits to households within pre-selected communities through the CDC. Within this sub-study, we will evaluate the socio-behavioral mechanisms of SARS-CoV-2 community transmission, including social interactions, health behaviors, healthcare utilization, knowledge, disease burden, and feasibility of at-home testing. The study hypothesis is that positive at-home test results will be associated with altered self-reported social interactions and altered health behaviors compared to negative test results. Surveys and questionnaires will be completed by participants through the smartphone app or via call center phone calls according to the schedule of events. Questionnaires will collect data on demographic characteristics, medical history and health status, COVID testing and symptoms, social interactions, knowledge of prevention strategies, infection risk, and attitudes towards vaccines.
Objectives:	
Primary Objective:
 
• To assess self-reported social interactions following SARS CoV-2 at-home test result over the study period 
Secondary Objectives:
 
• To assess change in self-reported behaviors before and following SARS CoV-2 at-home test result over the study period• To assess the impact of at-home testing regimen on self-reported healthcare utilization for SARS CoV-2 treatment• To assess knowledge of SARS CoV-2 prevention approaches over the study period
Endpoints:	
Primary Endpoint:
 
• Proportion of respondents that report adhering to social distancing guidelines after a test result; comparison of proportion adherent after positive vs. negative test result 
Secondary Endpoints:
 
• Proportion of respondents that decide to act on precautionary behaviors after a test result• Point estimate and 95% confidence interval for each healthcare utilization measure and composite measure• Proportion of respondents that are knowledgeable of precautionary measures to prevent infection• Prevalence of positive test results with 95% confidence intervals

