3 OBJECTIVES AND ENDPOINTS

Objectives	Outcome Measures	Endpoint
Primary		
1. To assess self-reported social interactions following SARS CoV-2 at-home test result over the study period	Assessments: self-reported data on social distancing, quarantine, social connectedness, healthcare utilization, well-being	Proportion of respondents that report adhering to social distancing guidelines after a test result for the entire study cohort and stratified by participant demographics (e.g., sex) of interest; comparison of proportion adherent after positive vs. negative test result
Secondary		
2. To assess change in self-reported behaviors before and following SARS CoV-2 at-home test result over the study period	Assessments: self-reported data on awareness of the issue, engagement, decisions to act, action, and maintenance	Proportion of respondents that decide to act on precautionary behaviors after a test result for the entire study cohort and stratified by participant demographics (e.g., gender) of interest
3. To assess the impact of at-home testing regimen on self-reported healthcare utilization for SARS CoV-2 treatment	Assessments: self-reported ED visits, hospitalizations, and ICU admission, for SARS CoV-2 evaluation or treatment	Point estimate and 95% confidence interval for each healthcare utilization measure and composite measure for the entire study cohort and stratified by participant demographics (e.g., gender) of interest
4. To assess knowledge of SARS CoV-2 prevention approaches over the study period	Assessments: self-reported data on perceptions and prevention of risks of contracting SARS CoV-2 infection	Proportion of respondents that are knowledgeable of precautionary measures to prevent infection for the entire study cohort and stratified by participant demographics (e.g., gender) of interest
5. Prevalence of positive test result for SARS CoV-2	Assessments: reported results of self-administered SARS CoV-2 antigen test	Prevalence of positive test results with 95% confidence intervals for the entire study cohort and stratified by participant demographic variables of interest

Exploratory		

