6. To assess the feasibility of at-home self-administered SARS CoV-2 antigen tests	Assessments: self-reported data on acceptability, practicality, integration, penetration, and demand of at-home self-administered antigen test	Proportion of respondents that find at-home self-administered antigen test acceptable for the entire study cohort and stratified by participant demographics (e.g., gender) of interest
7. To assess participant mobility following SARS CoV-2 at-home test results over the study period	Assessment: mobility patterns as captured by surrogates including activity trackers	Distribution of individual mobility data in response to positive vs. Negative SARS CoV-2 test results.
8. To assess attitudes towards SARS CoV-2 vaccination over the study period	Assessments: self-reported data on perceived susceptibility, severity, benefits, barriers, and cues to action related to SARS CoV-2 vaccination	Distribution of respondent's perception about SARS CoV-2 vaccination for the entire study cohort and stratified by participant demographics (e.g., gender) of interest

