9.1 STATISTICAL HYPOTHESES

The proposed analysis is primarily descriptive rather than inferential, as it designed to provide a general assessment of participant level behaviors in the context of a community testing intervention. An exploratory hypothesize is that positive at-home SARS-CoV-2 antigen test results will lead to altered self-reported social interactions and altered health behaviors compared to negative test results.

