9.4 STATISTICAL ANALYSES

9.4.1 GENERAL APPROACH

The approach to analysis will be primarily descriptive. Demographics, questionnaire data, and testing results will be reviewed and summarized using graphical techniques and summary statistics. Where applicable, exact method confidence intervals will be computed around point estimates. Trends over time will be evaluated graphically. The proportion of participants adhering to social distancing guidelines after a positive vs. negative test result will be compared using tests of proportion clustered by participants with various levels of intra-participant correlation. Stratified analyses by test or week number will also be performed. We will explore the associations between positive test results and critical behavioral measures using mixed modeling techniques to account for the participant and

household correlations. Analyses will be conducted using SAS (SAS Institute, Cary NC) and R with R Studio (R-project).

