9.4.3 ANALYSIS OF THE SECONDARY ENDPOINT(S)

- The first secondary objective is to assess change in self-reported behaviors before and following SARS CoV-2 at-home test result over the study period. This will be measured via Precaution Adoption Process Model Assessments of self-reported data on awareness of the issue, engagement, decisions to act, action, and maintenance. The proportion of respondents that decide to act on precautionary behaviors after a test result will be analyzed for the entire study cohort and stratified by participant demographics of interest (e.g., age, gender).
- The second secondary objective is to assess the impact of at-home testing regimen on self-reported healthcare utilization for SARS CoV-2 treatment. This will be measured via self-reported Emergency Department visits, hospitalizations, and ICU admission for SARS CoV-2 evaluation or treatment. The proportion of respondents that decide to act on precautionary behaviors after a test result will be analyzed for the entire study cohort and stratified by participant demographics of interest (e.g., age, gender).
- The third secondary objective is to assess knowledge of SARS CoV-2 prevention approaches over the study period. This will be measured via self-reported data on perceptions and prevention of risks of contracting SARS CoV-2 infection. The proportion of respondents that are knowledgeable of precautionary measures to prevent infection will be analyzed for the entire study cohort and stratified by participant demographics of interest (e.g., age, gender).
- The fourth secondary objective is to assess prevalence of positive test result for SARS CoV-2. This will be measured via self-reported results of self-administered SARS CoV-2 antigen test. The prevalence of positive test results will be analyzed with 95% confidence for the entire study cohort and stratified by participant demographics of interest (e.g., age, gender).

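### The precautionary-behavior endpoint pools positive and negative results, so by itself it cannot show the difference in health behaviors that the study hypothesis predicts

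*Combined protocol and SAP*

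**What the plan says.** The synopsis (1.1) states the study hypothesis: "positive at-home test results will be associated with altered self-reported social interactions and altered health behaviors compared to negative test results". Section 9.1 repeats both parts, labels the hypothesis exploratory, and says: "The proposed analysis is primarily descriptive rather than inferential".

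Section 3 attaches a contrast by test result to two endpoints. The primary endpoint, on social distancing, includes "comparison of proportion adherent after positive vs. negative test result". The exploratory mobility endpoint is "Distribution of individual mobility data in response to positive vs. Negative SARS CoV-2 test results".

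The endpoint for objective 2, on self-reported behaviors, is "Proportion of respondents that decide to act on precautionary behaviors after a test result for the entire study cohort and stratified by participant demographics", with no split by test result. The synopsis gives it without any split. The first bullet of 9.4.3 plans the same thing: "The proportion of respondents that decide to act on precautionary behaviors after a test result will be analyzed for the entire study cohort", again with demographic strata.

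One other sentence bears on the point. In 9.4.1 the plan says: "We will explore the associations between positive test results and critical behavioral measures using mixed modeling techniques", allowing for participant and household correlation. The measures are not listed.

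**The concern.** Half of the hypothesis is about health behaviors after a positive compared with a negative result. The endpoint that reports precautionary behavior averages over both kinds of result, so a strong reaction to a positive and no reaction at all can give the same reported value. Section 2.1 presents early detection leading to isolation and quarantine precautions as the purpose of frequent testing, so what people do after a positive result is a central link in the study's reasoning. Section 9.2 also expects the sample to describe behavioral change associated with test results. If the plan is followed as written, the figure reported for objective 2 will not do that. Any evidence on this half of the hypothesis would rest on an exploratory model whose outcomes have not been named in advance.

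**Working it through.** **1. The texts side by side**

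| Place | Quantity | Positive vs negative? |
|---|---|---|
| 1.1 and 9.1, hypothesis | Social interactions and health behaviors | Yes, for both |
| Section 3, objective 1; 9.4.2 | Adherence to social distancing | Yes |
| Section 3, objective 7 | Mobility | Yes |
| 1.1; Section 3, objective 2; 9.4.3, first bullet | Acting on precautionary behaviors | No; whole cohort, with demographic strata in Section 3 and 9.4.3 |
| 9.4.1, mixed models | Unnamed behavioral measures | Yes, exploratory |

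The other stratifications do not fill the gap. Section 9.4.8 stratifies by demographics. The stratification by test or week number in 9.4.1 concerns sequence, not result. The Schedule of Activities allows questionnaires after each test whatever the result, so both kinds of response enter the pooled figure.

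**2. The plan's own precision figures**

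Margin = 1.96 × √(p(1−p)/N). For p = 50% this gives 3.10, 1.39 and 0.98 points at N = 1,000, 5,000 and 10,000. Multiplying by the finite-population factor √((300,000−N)/(300,000−1)) gives 3.09, 1.37 and 0.96, which match the table in 9.2. These are margins for one proportion. Section 9.2 gives none for a difference by test result.

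**3. What the pooled endpoint identifies**

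Let q be the share of responses that follow a positive result, and let P₊ and P₋ be the proportions acting after a positive and a negative result.

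Pooled = q × P₊ + (1−q) × P₋

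This is one equation in two unknowns. With q = 5%, three quite different situations give a pooled value of 42.5%:
- P₊ = 90%, P₋ = 40% (difference +50): 0.05×90 + 0.95×40 = 4.5 + 38.0 = 42.5
- P₊ = P₋ = 42.5% (difference 0)
- P₊ = 4.5%, P₋ = 44.5% (difference −40): 0.225 + 42.275 = 42.5

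No increase in N separates them. This step does not depend on the true values of q, P₊ or P₋.

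**4. Illustration of size**

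The documents give no expected positivity and no behavior rates. Assume q = 1% to 5%, P₊ = 90% and P₋ = 40%. The shift is q × (P₊ − P₋). The last column is the margin for the direct difference at N = 5,000 with independent responses: 1.96 × √(0.9×0.1/(qN) + 0.4×0.6/((1−q)N)).

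| q | Pooled value | Shift from 40% | Positives at N = 5,000 | Margin for P₊ − P₋ |
|---|---|---|---|---|
| 1% | 40.5% | 0.5 points | 50 | 8.4 points |
| 3% | 41.5% | 1.5 points | 150 | 5.0 points |
| 5% | 42.5% | 2.5 points | 250 | 4.0 points |

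All three shifts are below the 3.09-point margin at N = 1,000. Against 1.37 (N = 5,000) and 0.96 (N = 10,000), only the 1% case is below; the 3% and 5% cases exceed both.

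**5. A less favorable case for the split**

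With 50% acting in both groups, the margin for the difference at N = 5,000 is 1.96 × √(0.25/50 + 0.25/4,950) = 13.9 points at q = 1%, and 6.4 points at q = 5%. At N = 1,000 it is about 31 and 14.2 points. The first of these rests on 10 positives, so the normal approximation is rough there.

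**The case against.** The strongest reply is that the plan already provides a by-result analysis of behavior. The mixed models in 9.4.1 relate positive results to behavioral measures, and 9.1 calls the hypothesis exploratory, so an exploratory model for an exploratory hypothesis is consistent. This stands, and it rules out a stronger reading that a reader might infer: that the study cannot address the second half of its hypothesis. It could. What is missing is any statement that precautionary behavior is among the modeled measures, or any link from that sentence to objective 2.

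A reader might also infer that health behaviors get no by-result endpoint at all. The documents do not support that either. They do not define health behaviors, and Section 2.2 counts social distancing among protective measures alongside masking and hygiene. The primary endpoint compares social distancing by result, so the gap concerns the remaining precautionary behaviors.

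Third, objective 2 is worded as change before and following a result, not positive versus negative. That is true, and the addition proposed here does not supply the before/after comparison. The hypothesis nevertheless asks for the by-result contrast, and this is the endpoint where one would look for it.

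Fourth, the illustration rests on assumed inputs, and it counts responses where the endpoint counts respondents. With testing three times a week for 4 weeks, the share of respondents with at least one positive can exceed the share of positive responses. Both points stand. The identification argument in step 3 uses neither the assumed rates nor the unit.

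Finally, Section 9 defers further detail to a separate analysis plan, which is not in the text available here. It may name the measures. The endpoint definition, however, belongs in Section 3 and the synopsis.

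**Conclusion.** The point holds in a limited form. The precautionary-behavior endpoint, as defined in the synopsis, Section 3 and 9.4.3, cannot by itself show the positive-versus-negative difference that the hypothesis predicts. That follows from its definition and needs no assumption. The only planned analysis that could show it for these behaviors is the exploratory model in 9.4.1, whose measures are unnamed.

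The statement that the pooled figure mostly reflects behavior after negative results is plausible under frequent screening but assumes low positivity, which the documents do not give. With 1% to 5% positive and 90% versus 40% acting, a 50-point difference moves the endpoint by 0.5 to 2.5 points. It would be wrong to infer that the shift is always lost in sampling error: at N = 5,000 or 10,000 it exceeds the plan's margin when 3% or 5% are positive. Even then it could not be attributed to positives without a figure for negatives alone.

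Because the study is descriptive and the hypothesis exploratory, this is a change worth making rather than a flaw that undermines the study.

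**What to change.** In the synopsis, in Section 3 under objective 2, and in the first bullet of 9.4.3, keep the pooled proportion and add three quantities: the proportion acting after a positive result, the proportion acting after a negative result, and their difference with a 95% confidence interval. Use the participant-clustered method that 9.4.1 already sets for the primary comparison. In 9.4.1, name precautionary behavior among the measures to be modeled.

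Test results and behavior questionnaires are already collected, so the cost is wording in four places and one further contrast. The estimate after a positive result will be less precise than the pooled figure, by an amount that depends on the number of positives. In the illustration at N = 5,000, the margin for the difference is about 8.4 points with 1% positive and 4.0 points with 5%. Allowing for repeated responses from the same participant may change these margins.

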4 STUDY DESIGN

4.1 OVERALL DESIGN

This is an observational, direct-to-participant, nested cohort, sub-study embedded within a public health intervention that distributes at-home, self-administered, SARS-CoV-2 antigen testing kits. Adults and children over 8 years of age living within the pre-identified communities will be included. This sub-study focuses on gathering participant-level data to evaluate behavioral determinants of home testing and socio-behavioral mechanisms of SARS-CoV-2 community transmission.

The smartphone application developed by CareEvolution, called MyDataHelps, will be used for this study, and it is free of charge on Apple or Android devices³. As part of the public health intervention, households will receive test kits and included in them will be information about the app and a QR code to facilitate access. Only after the participants have received information about the public health intervention and received the testing kits, will they be offered the option to participate in this sub-study. Once registered, if the participant wants to be a part of the sub-study, eligibility criteria will be verified and e-consent will be obtained through the app. The smartphone app includes instructions to administer at-home tests, for all participants in the public health intervention. Push notifications will be programmed with messaging to promote adherence including personalization, context, and timing for all participants in the public health intervention. Additionally, participants will have an option to opt-in to reminders for testing 3 times a week at a time of their preference. For participants who provide consent to the sub-study, the app will also feature the ability to report the results of their test results (upload images of test trips), track testing history, respond to surveys and questionnaires, and access study team's contact information. As an alternative to the app, participants can participate in the study via phone interviews conducted by a centralized study call center. Home test kits will include a QR code for the public health intervention app which will link to DCRI call center/eConsent for those interested in participating. Using scripted interview guides, call center staff will be ready to explain study participation, obtain verbal consent, administer study questionnaires including soliciting test results, and issue phone reminders for participants who chose not to use the study app.

Using PhenX and Common Data Element (CDE) measures, the surveys and questionnaires will collect data on demographic characteristics, medical history and health status, SARS-CoV-2 testing and symptoms, social interactions, knowledge of prevention strategies, and infection risk, and attitudes towards vaccines.

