Study Population:	Adults and children > 8 years of age living within pre-identified communities participating in the public health intervention
Phase:	Not applicable

Description of Sites/Facilities Enrolling Participants:	This is a site-less, direct to participant study. Participants, up to 300,000, will be recruited for the sub-study within the communities participating in the larger public health intervention.
Description of Study Intervention:	Collection of survey data
Study Duration:	Total of up to 29 weeks, including up to 4 weeks of screening period and 25 weeks from the start of the study.
Participant Duration:	Up to 25 weeks: 4 weeks of active testing period and 17 weeks of follow-up. Last follow-up will be at week 21 with a 4 week window (up to week 25) to complete the surveys.

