1.2 SCHEMA

1.3 SCHEDULE OF ACTIVITIES (SOA)

Study Period/Phase:	Screening & Enrollment Phase	Sub-study Questionnaires/Surveys							Comments & Notes	
		Testing Phase (Public Health Intervention)*				Follow-Up Phase				
Week:	Weeks-4 to 0	Baseline	Week 1	Week 2	Week 3	Week 4	Week 5	Week 13	Week 21	
Informed Consent and Assent when applicable		X								e-Consent via app or verbal consent via call center
Create mobile app account		X								For participants using the mobile app
Contact Information		X								
Socio-Demographic Data		X								
Medical History		X								
Anthropometrics – Weight		X				X				
Anthropometrics – Height		X								
Questionnaires										Questionnaires can be completed during the week after each test (regardless of the result).
• Social interactions		X	X		X		X	X	X	
• Behaviors										
• Symptoms										
• Healthcare utilization										
• Beliefs		X	X				X		X	
• Knowledge of prevention approaches							X		X	
• Feasibility of at-home testing							X			
Testing Adherence/Compliance reminders			X	X	X	X	X	X	X	

*The public health intervention (3 times a week at-home testing) does not require consent. Consent is only required for this sub-study which involves the questionnaires/surveys that are administered during the testing phase and follow-up phase.

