4.3 JUSTIFICATION FOR DOSE

There is no study specified administration of a test product. The SARS-CoV-2 test is being self-administered as part of the public health intervention, and is not part of this sub-study protocol.

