5.2 EXCLUSION CRITERIA

There are no exclusion criteria for this study, if all above inclusion criteria are met.

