10.1.1.2 CONSENT PROCEDURES AND DOCUMENTATION

Informed consent is a process that is initiated prior to the individual's agreeing to participate in the study and continues throughout the individual's study participation. Consent forms will be Institutional Review Board (IRB)-approved. Individuals participating via the app will be asked to read, review and electronically give their consent directly on the app. For individuals participating via the phone, the call center staff will explain the research study to the participant and answer any questions that may arise. A verbal explanation will be provided in terms suited to the participant's comprehension of the purposes, procedures, and potential risks of the study and of their rights as research participants. Participants will have the opportunity to ask questions prior to giving their verbal consent. Participants must be informed that participation is voluntary and that they may withdraw from the study at any time, without prejudice. The informed consent process will be conducted and documented, including the date consented, before the participant undergoes any study-specific procedures.

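### No rule places consent or Baseline before the first home test, so some participants may enrol already knowing a result, and nothing in the plan identifies them

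*Combined protocol and SAP*

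**What the plan says.** - **Offer.** Section 4.1 makes the sub-study available only after people have been told about the public health intervention and have "received the testing kits, will they be offered the option to participate in this sub-study". The kit also carries the app information and QR code.
- **Testing.** The footnote to the schedule in 1.3 reads "The public health intervention (3 times a week at-home testing) does not require consent". Section 4.3 adds that the test "is not part of this sub-study protocol".
- **Consent timing.** Section 10.1.1.2 requires consent "before the participant undergoes any study-specific procedures". By 4.3 the home test is not such a procedure.
- **Eligibility.** Section 5.1 asks for residence, age and consent. Section 5.2 states "There are no exclusion criteria for this study".
- **Timeline.** The synopsis gives a study duration "including up to 4 weeks of screening period". The schedule labels this period Weeks -4 to 0 and lists Baseline ahead of Week 1. Week 0 and Week 1 are not defined by the date of the first home test.
- **Result reporting.** Section 4.1: "For participants who provide consent to the sub-study, the app will also feature the ability to report the results of their test results".
- **Aim and endpoints.** The first secondary objective (Objective 2 in section 3) is to "assess change in self-reported behaviors before and following SARS CoV-2 at-home test result"; its listed endpoint is a proportion after a result. Prevalence of positive results is a further secondary endpoint. The primary endpoint includes a comparison of adherence after positive versus negative results.
- **Tracking.** Section 6.4 says departures from the testing programme will not be tracked.

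**The concern.** A household can open the kit and start testing on the day it arrives, then join the sub-study later, possibly because of what a test showed. Sections 9.4.1 to 9.4.3 have no rule for that case. Three quantities are exposed:

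- **Change around a result (aim of Objective 2).** A Baseline completed after a result may already show the altered behaviour, so a real change would be understated.
- **Prevalence.** If a known positive makes people more or less likely to enrol, the enrolled cohort does not have the community's positivity. A larger sample narrows the interval but leaves this bias unchanged.
- **Positive versus negative comparison.** If people who comply after a positive are also the ones who enrol, adherence after a positive is overstated. This affects only positives known at consent, so the exposure is smaller.

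**Working it through.** **Step 1: does any provision close the gap?** The consent rule in 10.1.1.2 covers study-specific procedures, and 4.3 takes the home test out of that class. Sections 5.1 and 5.2 do not mention earlier tests. The schedule's order shows intent, but its one note on questionnaire timing sets it relative to a test and states no pre-test condition for Baseline. No section tells households to wait, or says that the date or result of a kit test taken before consent is recorded. The gap is open.

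**Step 2: the plan's own precision figures (9.2).** Margin = 1.96 × sqrt(p(1−p)/n).
- n=1,000, p=1%: 1.96 × sqrt(0.01×0.99/1,000) = 0.62 points (table: 0.62).
- n=5,000, p=1%: 0.28 points (table: 0.27).

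The plain formula is within 0.02 points on all 12 rows. With a finite population correction sqrt((N−n)/(N−1)) and N=300,000, all 12 rows match to two decimals. For p=2%, which the table does not list, n=1,000 gives 1.96 × sqrt(0.02×0.98/1,000) = 0.87 points.

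**Step 3: prevalence.** The documents give no enrolment rates, so the inputs are assumptions: true prevalence p=2%, and positives enrol k times as often as others. Observed prevalence = kp/(kp+1−p).
- k=0.5: 0.01/(0.01+0.98) = 1.0%.
- k=2: 0.04/(0.04+0.98) = 3.9%.

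These apply k to every positive and assume that every positive is counted. If only half of positives are known before consent (assumption), the average ratio is (1+k)/2:
- k=0.5: ratio 0.75, 0.015/(0.015+0.98) = 1.5%.
- k=2: ratio 1.5, 0.03/(0.03+0.98) = 3.0%.

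If a pre-consent positive is never entered, enrolling that person does not raise observed prevalence unless they test positive again. Even the direction therefore depends on what is recorded.

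**Step 4: how much selection matters?** The ratio at which bias equals the tabulated margin m is k = o(1−p)/(p(1−o)), with o=p+m.
- n=5,000, p=1%, m=0.27: k = 1.27.
- n=5,000, p=10%, m=0.82: k = 1.09.
- n=1,000, p=1%, m=0.62: k = 1.63.

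**Step 5: before/after change.** If a fraction f of the relevant Baselines is post-result and already shows the change, the measured change is (1−f) times the true one. An assumed 20-point change becomes 18, 15 or 10 points for f = 10%, 25% or 50%. No listed endpoint is computed this way, so this bears on the objective only.

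**Step 6: adherence after a positive.** Assume true adherence of 50%, with adherent positives enrolling r times as often as non-adherent ones. Observed adherence = 0.5r/(0.5r+0.5), which is 55.6% for r=1.25 and 60.0% for r=1.5. This is an upper illustration, since positives obtained after enrolment are not subject to it.

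**The case against.** The case against has real substance.

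- **The intended order is Baseline first.** The synopsis adds the 4 screening weeks to 25 weeks from study start, giving 29, and the app that leads to enrolment also carries the test instructions. This stands: the fault is a missing rule. A reader might infer from the length of the window that enrolment is planned to run alongside the 4 weeks of testing. The documents do not support that.
- **Earlier results may be captured.** A reader might infer from 4.1 that results before consent are lost. The text says only that the reporting feature comes with consent. The app tracks testing history, the call center asks for results, surveys cover testing (4.1), and app entries have an audit trail (10.1.9.1). The questionnaires are not in the documents, so the needed items may already exist.
- **A later negative is a genuine negative.** A reader might infer that a person positive before consent and negative afterwards is put in the wrong group. The comparison is by test result, clustered by participant (9.4.1), so this is carryover of behaviour and not misgrouping.
- **The per-protocol set may drop late enrolees.** Section 9.3 requires testing three times a week for 4 weeks plus the surveys. This helps in part, but it rests on self-report and does not link tests to the enrolment date. The modified sets admit anyone with one test or one survey.
- **Other surveys can serve as the before value.** Surveys recur at Weeks 1, 3 and 5, so a later positive can have an earlier in-study survey. This stands, and the fix uses it.
- **The analysis is mainly descriptive, with detail deferred to a separate plan (9, 9.1).** That lowers the stakes, but a later plan cannot recover a test date that was never collected.

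**Conclusion.** The point holds as a missing rule and a missing data item. As written, the plan can enrol people who already know a result, can record their post-result answers as Baseline, and states no way to tell them apart. The consequences are an invalid before value for the aim of Objective 2, a possible bias in prevalence, and a smaller possible bias in the positive-versus-negative comparison.

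How often this would happen is unknown. Under the assumed ratios of 0.5 and 2, a true 2% is seen as 1.0% or 3.9% if all positives are affected, and as 1.5% or 3.0% if half are. The corresponding sampling margin is about 0.87 points at N=1,000. The margin of 0.62 in 9.2 belongs to a 1% proportion and is not the right comparator. The table in 9.2 describes sampling error only and does not claim to cover selection. Nothing in the documents shows that late enrolment will be common.

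**What to change.** 1. Unless the questionnaires already capture it, add to Baseline the date of the first home test from the kit, the number of kit tests already taken, and whether any was positive.
2. In the analysis plan, accept a survey as the before value only if it was completed before the result in question.
3. Report the prevalence, before/after and positive-versus-negative analyses also restricted to participants enrolled before their first result, or to results obtained after enrolment, and show later enrolees separately. For prevalence the first restriction is cleaner, because someone who joins after a positive may test positive again.

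The cost is two or three survey items, some analysis wording, and wider margins in the restricted analyses, by an amount that depends on how many enrol late. No one is excluded from the study, and the survey schedule need not be re-anchored to the first test. If early testing proves rare, the new items will show that.
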